12.0 Provisions to Monitor the Data to Ensure the Safety of Subjects

A Data Safety Monitoring Board (DSMB) will monitor safety throughout the study. Please see separate Data Safety Monitoring Board (DSMB) charter. The DSMB charter will be a living document that can be modified during the study.

The DSMB will meet at least every six months during the study. The DSMB will review and approve the protocol prior to beginning data collection. They will decide on stopping criteria for the study. The biostatisticians and data manager will work with the DSMB to perform interim analyses. Adverse events will be monitored continuously.

throughout the study and will be reported to the DSMB in a timely manner according to pre-specified requirements. Analyses for each DSMB meeting will be completed according to the requests of the DSMB. Investigators and DSMB members will be blinded to group assignment. Adverse event rates and interim study results will be reviewed and discussed by the DSMB at the DSMB meetings. At least four categories of adverse events will be defined: a) death; b) cardiovascular events (myocardial infarction, stroke, and coronary arrhythmias); c) hospitalizations; and d) injury or illness causing chronic disability. We will report all serious adverse events to the DSMB in a timely fashion. In addition to these serious adverse events, we will monitor participant weight and blood pressure during monthly visits throughout the study. We will use a designated data collection form to record these events. As noted above, however, we anticipate that that epicatechin-rich cocoa beverage will have few significant adverse events.

13.0 Withdrawal of Subjects

- 13.1 Anticipated circumstances under which subjects will be withdrawn from the research without their consent, including stopping participation for safety reasons.* We anticipate that subject withdrawal from the research without their consent will be infrequent. However, a potential example is if a participant develops symptoms during the study and the Principal Investigator feels that the symptoms could make the study unsafe for the participant to continue. In this circumstance, the participant would be advised to follow-up with their physician. If the participant refuses to follow-up with their physician, it may be necessary for the participant to be withdrawn without their consent.
- 13.2 Procedures when subjects withdraw from the research.* Subjects may withdraw from the research at any time. If they decide to leave the research, they should contact the principal investigator, [name]. If they stop being in the research, already collected data may not be removed from the study database. They will be asked whether the investigator can collect data from their routine medical care. If the subject agrees, this data will be handled the same as research data.

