Randomization. Participants will be randomized to either epicatechin-rich cocoa intervention or placebo using a SAS computer program. We will use block randomization with block sizes randomly selected from 4 and 6 to ensure balance. Randomization will be stratified according to baseline six-minute walk performance.

Monthly assessments to monitor adherence. Participants will attend monthly study visits to receive their monthly supply of beverages.

Participants will be asked to bring any remaining beverage packets from the previous month. Packets will be counted and the number of packets remaining from the previous month will be recorded. Participants will be asked to keep a log of their study beverage consumption and will be asked to turn in their log at each monthly visit. Participants will be asked to bring their current medications to these monthly meetings and changes in medication from the previous month will be recorded. In addition, weight and blood pressure will be measured at each monthly visit. If participants are having difficulty adhering to the beverages, staff may call participants in between monthly visits to check in on adherence and to remind them to fill out their monthly adherence log.

Monitoring diet and weight gain. Participants will receive a handout about monitoring and controlling their weight during the study. Participants in the intervention and control groups will be asked to weigh themselves approximately daily and record their weight on a data collection form. Participants who do not have access to a scale will be provided with a scale. They will be asked to bring this weight chart to each monthly visit. Participants observed to gain five percent or more of their body weight compared to baseline during the study will be evaluated by the study team for possible causes of weight gain. If the weight gain is determined due to increased caloric intake (rather than fluid weight gain), they will receive dietary counseling in effort to avoid additional weight gain and to advise them on dietary methods to help with weight control. Study beverages will be reduced or discontinued if a participant gains 20 or more pounds during the study.

Six-month follow-up testing. After six months of participation in the study, participants will be asked to return for follow-up testing. All measures and tests that were conducted at baseline will be repeated.

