The six-minute walk and brachial artery FMD will be measured while off of study beverages for 2.5 hours and 24 hours, respectively. . The treadmill stress test will be measured while off of the study beverages for 48 hours. The calf muscle biopsy will be performed after other outcome measures are complete and while on study beverages whenever possible. If extenuating circumstances prevent outcome measurement in these defined time frames, the measurement will be obtained as close as possible to the desired time point/length of time after the final cocoa dose.

Some or all study measures may be repeated at baseline or follow-up for data quality (e.g. if a treadmill test must be stopped due to extremely high blood pressure before the patient completed the test is one potential example of why a measure may need to be repeated).

In some cases, participants may be asked to take study beverages for longer than six months. For example, if a participant has an illness that prevents them from returning at six months for follow-up testing or if they are out of town during their six-month follow-up window. In these instances, participants will be asked to continue taking their study beverages for more than six months. Participants may be asked to take up an additional two months of study beverages.

9.2 *Research procedures.*

Ankle Brachial Index (ABI). After the participant rests supine for five minutes, the right brachial, dorsalis pedis (DP), posterior tibial (PT) and left DP, PT, and brachial artery pressures are measured using a hand-held Doppler probe. Pressures are measured twice. The ABI is calculated for each leg by dividing the average of the DP and PT pressures by the average brachial pressure (59). If a participant qualifies for a heel-rise ABI based on their initial ABI, they will be asked to perform 50 heel-rises at a rate of one per second followed by additional measurements of the right and left brachial, DP, and PT pressures.

Questionnaire Administration. Participants will be administered IRB-approved study questionnaires by a trained and certified study coordinator.

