11.0 Data and Specimen Management

11.1 Data management.

Data is recorded using preprogrammed instruments and an electronic case report form using secure, HIPAA-compliant REDCap database software on servers maintained by Northwestern's Clinical and Translational Sciences Institute. We have substantial experience with REDCap.

11.2 Power Estimates/Calculations.

The COCOA-PAD Study is a pilot study intended to collect preliminary data to estimate an effect size and to assess the feasibility of our proposed methods. Therefore, we calculated the sample size that allows us to identify an effect size estimate. Our power calculations anticipate a < 10% drop-out rate at 6-month follow-up, based on data from our completed GOALS and SILC randomized trials in PAD participants (34,60). For our primary aim, we will compare changes in six-minute walk performance at 6-month follow-up between the epicatechin-rich cocoa group and the placebo group. Comparisons will be made for measures obtained both while off of the study beverages for 2.5 hours and while off of the study beverages for 24 hours, respectively, in order to assess both acute and chronic effects of cocoa on six-minute walk. A total of 40 participants completing the trial will provide a two-sided 95% confidence interval (CI) with a margin of error of 0.64 standard deviation (SD) for the effect size in change of six-minute walk performance between the cocoa (n=20) and the placebo groups (n=20). Using the estimated SD from our SILC trial (34), the margin of error of 0.64 SD represents approximately 33 meters. Prior studies have defined clinically meaningful changes in the six-minute walk as 20 meters (small meaningful difference) and 50 meters (large meaningful difference) (73,74). Similarly, 40 participants completing the trial provides a two-sided 95% CI with a margin of error of 0.64 SD for the effect size in 6-month change of each secondary outcome between the cocoa and placebo groups.

Statistical Analyses. Data will be analyzed according to each participant's originally assigned group, irrespective of whether the participant adheres to his/her assigned group (i.e. intention to treat principle). For our Primary Aim, we will use a t-distribution to obtain the 95% CI for the difference in changes in six-minute walk performance at 6-month follow-up between the

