23.0 Local Number of Subjects

We will identify and randomize 44 eligible participants.

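### Once a participant leaves the research only routine-care data are requested, so the primary six-minute walk is not sought from them; for those who only stop the beverage, the 2.5 h and 24 h walk conditions are undefined

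*Combined protocol and SAP*

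**What the plan says.** Section 11.2 (Statistical Analyses) commits to intention to treat: data are analysed by assigned group "irrespective of whether the participant adheres to his/her assigned group". The primary endpoint in section 8.0 is the six-month change in the six-minute walk. Section 9.2 defines that walk as a scripted test in a 100-foot hallway and lets only that course count for the primary outcome.

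The protocol foresees two different departures.

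- **Leaving the research.** Section 13.1 allows the investigator to remove someone who develops symptoms and declines to see a physician: "it may be necessary for the participant to be withdrawn without their consent". Section 13.2 keeps data already collected and then says of those who leave: "They will be asked whether the investigator can collect data from their routine medical care". Neither section offers a six-month study visit.
- **Stopping the beverage.** Section 9.1 (Monitoring diet and weight gain) states: "Study beverages will be reduced or discontinued if a participant gains 20 or more pounds during the study". Section 9.2 (Dietary counseling and weight monitoring) repeats the rule. Neither passage says that these participants leave the study, and the six-month testing paragraph of 9.1 recalls participants without requiring that they still drink the beverage.

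The follow-up measurements are timed in hours since the last beverage, and section 11.2 compares the walk at both 2.5 h and 24 h. If circumstances prevent this, section 9.1 says "the measurement will be obtained as close as possible to the desired time point/length of time after the final cocoa dose". Section 11.4 (Missing Data) expects loss to be small, gives no method for a missing walk, and makes the analysis of those with at least 80% adherence a sensitivity analysis.

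**The concern.** An assigned-group analysis needs the outcome at six months from everyone randomised, as far as it can be obtained. Someone who leaves but would willingly return for one walk is not asked. The one thing requested, routine-care data, cannot be expected to contain the primary outcome. The loss is therefore partly created by the procedure, and no analysis method can fully replace a walk that was never attempted.

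Such losses may be related to the outcome. The protocol's own example of involuntary withdrawal is new symptoms, which could plausibly go with poorer walking. If losses of this kind fall unevenly between arms, a comparison of the observed walks is biased.

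A second, smaller gap affects participants who stopped the beverage weeks or months earlier and attend at month 6. They are neither 2.5 h nor 24 h from a dose. The plan does not say whether their walk enters the acute comparison, the chronic comparison, both or neither, so staff and analysts could settle this differently from case to case.

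**Working it through.** **1. The plan's own figure.** Inputs: "We will identify and randomize 44 eligible participants" (section 23.0); 40 completers, 20 per arm (11.2); "Our power calculations anticipate a < 10% drop-out rate at 6-month follow-up" (11.2).

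- Loss allowed for: (44 − 40)/44 = 9.1%, consistent with under 10%.
- Half-width of the two-sided 95% interval: t(0.975, 38) × √(1/20 + 1/20) = 2.024 × 0.3162 = 0.640 SD. The stated 0.64 SD is reproduced.
- Implied SD of change: 33 m / 0.64 = 51.6 m, so 0.640 × 51.6 = 33.0 m, as stated.

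**2. Precision cost.** With all 44 walks (22 + 22, assuming 1:1 allocation) the half-width is 0.608 SD, or 31.4 m, against 33.0 m with 40. Under the one-sided 90% limit adopted in section 11.3, the margins are 20.2 m and 21.3 m. The difference is small and already planned for.

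**3. Possible bias.** Suppose k of 22 in an arm have no walk and their mean change is D metres worse than that of the arm's completers. The mean over all 22 is then the completers' mean minus (k/22) × D. If D is the same in both arms:

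bias in the difference = (k_cocoa − k_placebo)/22 × D

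The documents give no value for D. I assume 20 to 60 m, which is 0.39 to 1.16 of the implied SD (20/51.6 and 60/51.6).

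| Lost, cocoa : placebo | D = 20 m | D = 60 m | Share of 20 m |
|---|---|---|---|
| 2 : 2 | 0 | 0 | 0% |
| 3 : 1 | 2/22 × 20 = 1.8 m | 2/22 × 60 = 5.5 m | 9–27% |
| 4 : 0 | 4/22 × 20 = 3.6 m | 4/22 × 60 = 10.9 m | 18–55% |

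Losing poorer walkers from cocoa flatters cocoa; reversing the split reverses the sign. The 20 m is the small meaningful difference named in section 11.2.

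**4. Beverage stoppers, passages side by side.** Section 9.1 recalls participants at six months with no adherence condition. Section 11.2 analyses them whatever their adherence. Section 11.4 removes low adherers only in a sensitivity analysis. So a walk at month 6 is expected from them. What is missing is its label: the fallback in 9.1 names a time point and a length of time since the last dose together, and for an early stopper these two targets cannot both be approached. The only remedy 9.1 gives for a missed window, up to two more months of beverages, assumes the participant is still taking them.

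**The case against.** A reader might infer that anyone who stops the beverage has no valid six-month walk, or that the fallback sends a participant who stopped in month 2 for testing near month 2. The documents support neither. Stoppers are recalled at six months and belong in the main analysis. The fallback sits in the six-month testing text and addresses extenuating circumstances; no passage orders early testing or gives a beverage to someone who has been discontinued. Section 13.2 concerns only people who leave the research, and section 11.4 lists loss to follow-up and non-adherence as separate items.

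The size can also be challenged, and much of that challenge stands. D is an assumption, and its upper end exceeds one implied SD. Four is the total drop-out allowed for, not the number that section 13.2 causes. Section 13.1 expects involuntary withdrawal to be infrequent. The trial is double-blind, the drinks match in calories, and the weight rule applies to both arms, so an even split with no bias is quite possible.

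Finally, section 11.3 records that recruitment was complete when it was written, so new consent wording could mean contacting participants again. The consent pages are not in the review copy, so what participants were told about follow-up after leaving cannot be judged.

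None of this answers the central point: the primary outcome is not requested from those who leave, and nothing in the plan takes its place.

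**Conclusion.** The point holds in two parts of unequal weight. The main part is that sections 13.1 and 13.2 seek no six-month walk after a participant leaves or is withdrawn, which sits poorly with the intention-to-treat commitment and the absence of a missing-data method. The lesser part is a clarification: the 2.5 h and 24 h conditions are undefined for those who stopped the beverage early.

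The bias is between 0 and about 11 m in either direction, up to roughly half of the 20 m small meaningful difference. This rests on 22 per arm, at most 4 lost, a common shortfall of 20 to 60 m in both arms, and splits from 2:2 to 4:0. If the shortfall differed between arms, an even split would not guarantee zero. The issue does not invalidate the trial, but the change is inexpensive and worth making in a study of 44.

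**What to change.** 1. In sections 13.1 and 13.2, separate stopping the study beverage from leaving outcome follow-up.
2. Ask everyone who leaves or is withdrawn whether they will still attend one month-6 visit for the six-minute walk, where the investigator considers testing safe, in addition to the routine-care request.
3. State that these walks enter the assigned-group analysis.
4. Reconcile the timing rule and fallback in section 9.1 with the beverage discontinuation foreseen in 9.1 and 9.2. Keep the test at six months, record the time since the last beverage, and say how such a walk is classified in the acute and chronic comparisons. How beverages are handled, and which comparison these walks join, is for the sponsor to settle.

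The cost is protocol and possibly consent wording, and a few follow-up visits. Including walks from people no longer on the beverage may make the estimated effect slightly smaller. Only some missing walks would be recovered, so section 11.4 would still lack a statement on those that remain missing. If six-month testing has already ended, the change can serve only the definitive trial that this pilot is meant to inform.

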14.0 Risks to Subjects

The placebo beverage has the same caloric intake and nutritional characteristics as the cocoa beverage except that the placebo drink contains no cocoa or flavanols. In general, older patients with PAD have a high prevalence of comorbid diseases, particularly coronary artery disease, cerebrovascular disease, diabetes mellitus, and pulmonary disease. Thus the patient population is likely to be of generally poorer health than that of older men and women without PAD in the general population.

Risks associated with cocoa therapy. Cocoa is the dried and fermented seed from *theobroma cacao*, from which chocolate is made. Epicatechins are flavanols and a major ingredient of cocoa that has therapeutic effects on skeletal muscle and the vasculature (21-30). Our cocoa-beverage intervention is a food product, manufactured by the Hershey Company. Similar cocoa drinks are widely available for commercial use. The flavanol epicatechin, when administered in therapeutic doses for research purposes, can cause lowering of blood pressure (76). Thus, blood pressure levels will be measured monthly during the study. The epicatechin-rich cocoa drink and the placebo will each deliver approximately 180 calories per day in the doses prescribed (three drinks per day). Weight will be monitored monthly throughout study participation.

Risks associated with the muscle biopsy. The muscle biopsy is associated with several potential risks. These include discomfort during the muscle biopsy procedure and immediately afterward, scarring from the muscle biopsy skin incision, bleeding, and infection. In addition, potential participants who are asked to hold their anti-platelet therapy during the week leading up to the muscle biopsy procedure may experience a cardiovascular event related to the temporary discontinuation of the anti-platelet therapy. First, to minimize risk related to muscle biopsy, all participants undergoing muscle biopsy will receive a written hand-out regarding signs to watch for that may indicate wound infection. They will also be verbally instructed in this. Each participant will be instructed to call [name] immediately if any signs of infection occur. Participants will be telephoned approximately seven days after the muscle biopsy and asked for any symptoms that may suggest an infection or delayed healing. Second, permission from the participant's physician will be required before participants are asked to discontinue anti-platelet therapy.

Six-minute walk test, four-meter walks, balance, and chair stands. The physical functioning tests may be associated with muscle fatigue or soreness. These symptoms typically resolve with rest.

These tests may be associated with the risk of falling or coronary ischemia or dyspnea due to heart failure or lung disease. Rarely, falling may result in a fracture. However, the research assistant who will collect these data has been trained to prevent falling. The risk of a fracture secondary to a fall during the testing is less than 1 in 5,000. If a participant experiences chest pain, research assistants are trained to page [name] immediately. If the chest discomfort does not immediately resolve with rest, participants are escorted to Northwestern's Emergency Department, which is located in the same building as the location of the tests. [name] facilitates follow-up, by contacting participants' physicians, for those who experience new

chest discomfort during testing. In our experience, the risk of chest discomfort is approximately 1 in 750.

Risks associated with ABI measurement. The ankle brachial index measurement consists of measuring systolic blood pressure in each extremity using a hand-held Doppler. The ABI is non-invasive, safe and does not have any known lasting side effects. During the ankle brachial index test, participants may experience discomfort from the inflated blood pressure cuff. However, this discomfort resolves immediately when the cuff is released.

Risks associated with questionnaire administration. Participation includes a risk of loss of confidentiality regarding personal health information. However, all research staff have undergone formal human subjects training. They are trained to protect the privacy of research subject participants.

Risks associated with drawing blood. The potential risks of drawing blood include a bruise at the site of vein puncture, inflammation of the vein, and infection. Participants undergoing a blood draw may experience lightheadedness, dizziness, or fainting.

Risks associated with MRI testing. The MRI scanner makes loud banging noises while doing a measurement. Participants will be provided with earplugs or earphones to protect against the noise. MRI testing can be difficult for people with claustrophobia. Potential participants who are claustrophobic will not be encouraged to participate in MRI testing.

15.0 Potential Benefits to Subjects

Participants who are randomized to the intervention could experience improved functional performance and prevent mobility loss, if our hypotheses are correct.

If the COCOA-PAD Study supports our hypotheses, results will be used to design a large, definitive randomized controlled trial of epicatechin-rich cocoa to improve lower extremity functioning and prevent mobility loss in the large and growing number of older people who are disabled with PAD.

